**Module 1: Gratitude-based activities**

**Week 1: Gratitude for positive events.**

Participants recall three events, small or large, in the preceding week that were associated with satisfaction, happiness, pride, or other positive states.

**Week 2: Expressing gratitude.**

Participants write a letter of gratitude thanking a person for an act of kindness; participants may, at their discretion, share the letter with the other person.

**Module 2: Strength-based activities**

**Week 3: Remembering a past success.**

Participants recall a prior event in which they experienced success. They write about the event, their contribution to the success, and the positive feelings evoked by recalling it. Finally, they consider how they might use the experience to be successful in the future.

**Week 4: Using personal strengths.**

Participants choose a personal strength that is important to them and then find a new way to use that strength over the following week.

**Week 5: Using Perseverance**

Participants work to learn the skills of sticking with something when things get though especially as it pertains to their recovery from the transplant.

**Module 3: Meaning-based activities**

**Week 6: Enjoyable and meaningful activities.**

Participants complete a series of self-selected activities that vary between those that bring immediate boosts in mood and those that are more deeply meaningful.

**Week 7: The Good Life**

Participants work to articulate what their values are and what their perception of a good life will look like especially as it pertains to their health and recovery.

**PROTOCOL TITLE: Development of a positive psychology intervention to improve mood and health related quality of life in patients post hematopoietic stem cell transplantation- Proof of Concept Trial**

**Week 8: Planning for the Future.**

Participants work to perform enjoyable and meaningful acts for themselves and others in daily life. Trainers help participants create a plan for using these skills on their own in the near future.

**Follow-Up Session**

At the last week of the study, a member of the study staff will call participants to repeat the self-report questionnaires that were administered at baseline. Positive and Negative Affective Scale (PANAS) to measure positive affect, Life Orientation Test-Revised [LOT-R] to measure optimism and the Hospital Anxiety and Depression Scale [HADS] to measure anxiety and depression. We will also assess HSCT-specific HRQoL with the Functional Assessment of Cancer Therapy-Bone Marrow Transplantation [FACT-BMT] scale), fatigue (PROMIS-Fatigue-8a) and overall function (PROMIS-PF-20). Finally, patients will be asked about their experience in the study, including any aspects of the intervention or study procedures that could be improved. In sum, these scales should take approximately 30-40 minutes to complete. If participants would rather complete the follow-up questionnaires in written form rather than over the phone, we will send them a paper packet at the time of the follow-up.

Given the results of our prior PP studies in medical populations yielding a 64-85% completion rate of the exercises, and given that this is a feasibility study (i.e., we want to assess participants' willingness to complete the phone sessions), we will expect participants to complete at least 5 PP exercises. In other words, if a participant completes at least 5 sessions, missed sessions will not be considered a deviation from the protocol.

**Training.** The PP exercises for this trial have been identified via published literature, or directly from researchers, and modified appropriately for this population based on results from first phase of the study that the IRB approved (17-154). Additional text outlining the rationale and instructions for each exercise are in the written packets for each exercise that are provided to participants. [name] will engage in several training exercises prior to study initiation. [name] research mentor, [name], and his research group have had substantial experience in explaining and delivering PP exercises from their studies in cardiac and psychiatric patients, which will inform [name] training. Together with [name], [name] will review the treatment manual and the team's prior training manuals related to these exercises. They then will complete all exercises together to gain experience performing and reviewing each exercise.

*9.3 Procedures performed to lessen the probability or magnitude of risks.*

**Confidentiality.** As with any study, there is the risk of a breach of confidentiality; these risks will be minimized by using participant identification numbers rather than

**PROTOCOL TITLE: Development of a positive psychology intervention to improve mood and health related quality of life in patients post hematopoietic stem cell transplantation- Proof of Concept Trial**

identifying personal data on study documents, and by using locked cabinets/offices and password-protected databases to store personal information. Only study staff (the PI, the research assistant entering data) will have any access to personally identifiable information about participants, and such access will be limited only to information necessary to complete study tasks. We will ensure that contact with participants is confidential by using only the phone numbers and other contact information that are specifically allowed by the participants and not leaving study-related messages for participants unless expressly allowed by participants. Upon enrollment, we ask all participants if it is acceptable to leave voice messages on their phones, as well as the appropriate times to call them. We adhere to any and all patient requests regarding contact.

Digital recordings of the sessions will be completed using portable recorders. If a study participant were to refuse audio recordings, they can either remove themselves from the study or work with the study investigator to choose an alternative to audio recording such as transcription. The principal investigator and the senior research mentor will randomly-select recorded phone sessions to review for competence and adherence to the protocol. All recordings will be downloaded immediately from the recorders and the electronic files will be kept within the firewalled, password-protected file on a Partners server. Recordings will contain no personally identifiable information (and principal investigator will not use names or other identifying information on the recordings) and will be erased following review.

**Informed consent process.** Regarding the consent process, we will approach/recruit participants in the hospital only after their clinicians in the HSCT transplant team have approved for them to be approached. When discussing the study, we will emphasize the study's optional nature and participants' ability to opt out/un-enroll at any time, for any reason.

**Medical & psychiatric emergencies.** If patients report acute medical symptoms, they will be directed to emergency medical care, and their primary medical physicians may be contacted as needed. If study staff have questions regarding medical symptoms and their urgency, patients' primary oncologist and their HSCT clinicians and the PI will be available to consult (and call patient) as needed. We will ask participants to report adverse events related to study participation they may have experienced at any time throughout the study.

We will obtain data using different measures as listed below. We will also check the patient electronic medical records to confirm baseline demographic information. The measures we will use are as follows:

- Optimism: LOT-R
- Positive affect: Positive Items on the PANAS
- Anxiety/depression: HADS
- HSCT-related QoL: FACT-BMT

**PROTOCOL TITLE: Development of a positive psychology intervention to improve mood and health related quality of life in patients post hematopoietic stem cell transplantation- Proof of Concept Trial**

- Overall function: PROMIS-PF-20
- Fatigue: PROMIS-Fatigue-8a

*9.4 Long-term follow-up.*

This study does not have long-term follow-up as part of the protocol. As aforementioned, the last week of the program entails obtaining some feedback about patient's perception of the intervention, as well as a repeat of the baseline questionnaires.

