**7.0 Study Timelines\***

*7.1 Subject Participation in the study*

The planned duration of total participant participation in the intervention is 24 weeks, broken down as follows: at weeks four, eight and twelve following consent and eligibility determination, participants will receive check-in/psychosocial support phone calls about their recovery, then week 14 is for self-assessment questionnaires prior to the 8-session weekly positive psychology treatment, and the last week will be used for a repeat of self-report measures obtained at baseline. Patients will also be given the option to complete self-reported measures via mail vs. phone.

**PROTOCOL TITLE: Development of a positive psychology intervention to improve mood and health related quality of life in patients post hematopoietic stem cell transplantation- Proof of Concept Trial**

Based on prior recent experience with recruitment from this patient population, we anticipate about 6-months for the total number of patients for the study.

We are estimating the study will be completed in June 2019.

	Enrollment	Check-In/Psychosocial support phone calls (weeks, 4, 8, 12)	Pre-Intervention Visit	Week 1 of PP-intervention	Week 2 of PP-intervention	Week 3 of PP-intervention	Week 4 of PP-intervention	Week 5 of PP-intervention	Week 6 of PP-intervention	Week 7 of PP-intervention	Week 8 of PP-intervention	Follow-Up Session
HSCT team meeting review to confirm eligibility	X											
Assessment of inclusion criteria	X											
Obtain Consent	X											
10-min phone call		X										
PP exercise				X	X	X	X	X	X	X	X	
Follow-up session												X
Self-report measures (LOT-R, PANAS, HADS, PROMIS-PF-20, PROMIS-Fatigue-8a, FACT-BMT)	X		X									X

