## 9.0 Procedures Involved\*

### 9.1 Study Design

**PROTOCOL TITLE: Development of a positive psychology intervention to improve mood and health related quality of life in patients post hematopoietic stem cell transplantation- Proof of Concept Trial**

The goals of this study are to assess the feasibility, acceptability and preliminary impact of this novel 8-session weekly PP-based intervention for HSCT patients.

Patients will be approached close to their discharge from the hospital after their HSCT for eligibility determination and to obtain consent. After consent is obtained, eligibility will be determined with the mini international neuropsychiatric interview (MINI) and a brief cognitive assessment (with the BIMS) to exclude patients who need more intensive psychological or psychiatric care or have cognitive deficits. Upon agreement and consent to participate in the study, participants will receive check-in/psychosocial support phone calls at weeks four, eight and twelve to provide support and check-in on how their recovery is going since discharge, develop rapport and prepare them for the positive psychology treatment portion of the intervention which will start between Day 90-120 post HSCT. Between the 90-120-day point, when patients return to the clinic for their routine 100-day post HSCT follow-up, the interventionist/principal investigator will meet briefly with the patients in clinic to complete self-assessment questionnaires to measure positive affect, optimism, anxiety, depression, HSCT-specific health related quality of life, adherence and overall function. For the rare situations when participants cannot complete these self-assessment questionnaires in person, patients will be given the option to complete self-assessment questionnaires by phone or mail.

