## 9.2 *Research Procedures*

**Psychosocial Support/Check-In phone calls:** Study participants will receive monthly phone calls from the study interventionist/principal investigator at weeks four, eight and twelve following their enrollment. The goal of the psychosocial support/check-in phone calls is to provide study participants an avenue to talk about their adjustment and transition to the outpatient care from inpatient, quality of life and coping during recovery, adherence to treatment, etc...which will be beneficial to patients

**PROTOCOL TITLE: Development of a positive psychology intervention to improve mood and health related quality of life in patients post hematopoietic stem cell transplantation- Proof of Concept Trial**

and help with rapport building with the interventionist prior to the positive psychology intervention.

**Pre-intervention visit:** The first physical contact with the patient since consent and enrollment during the HSCT hospitalization will be at the routine 100-day follow-up visit (around Day 90-120) in clinic. The visit will happen in a private room at in the DFCI outpatient clinic. Patients will complete the following self-assessment scales: Positive and Negative Affective Scale (PANAS) to measure positive affect, Life Orientation Test-Revised [LOT-R] to measure optimism and the Hospital Anxiety and Depression Scale [HADS] to measure anxiety and depression. We will also assess HSCT-specific HRQoL with the Functional Assessment of Cancer Therapy-Bone Marrow Transplantation [FACT-BMT] scale), overall function (PROMIS-PF-20), and fatigue (PROMIS-Fatigue-8a). Data about medical and oncologic history, treatment course and medications will be obtained from the electronic medical record. – A waiver of HIPAA authorization would be requested for this and will only be clarified with patients if there are inconsistencies in the medical records. This in person session should take about 30 minutes. Patients will also be given the option to complete this visit over phone if in person visit cannot be coordinated with other routine 100-day follow-up care.

After completion of the questionnaires, participants will be provided with a treatment manual, with weekly PP exercises. Participants will be assigned the first exercise (gratitude for positive events) in preparation for their first phone session.

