**Weekly phone sessions for positive psychology intervention:** All participants will be asked to complete 8 weekly PP exercises and to speak with the interventionist weekly. Weekly phone sessions will last approximately 30 minutes. Prior to completing each phone session, participants will be asked to rate their current level of happiness and optimism, using a 10-point Likert scale. Immediately after completing the exercise and phone session, participants will rate the ease of exercise/session completion, overall utility of the exercise/phone session, and their current levels of happiness and optimism, all using 10-point Likert scales. These calls will be recorded so that a percentage (10%) of these recordings can be reviewed by research mentor, [name] to ensure that the PP intervention is being delivered as described in the protocol.

**Follow-up session:** The last week of the study will be used for a repeat of the self-assessment questionnaires obtained at the beginning of the study. This will be done either via phone or mail depending on patient preference.

**Positive Psychology Program Content.** All phone sessions will include (a) a review of the ease and utility of the week's PP exercise (b) a discussion of the

**PROTOCOL TITLE: Development of a positive psychology intervention to improve mood and health related quality of life in patients post hematopoietic stem cell transplantation- Proof of Concept Trial**

rationale of the next week's PP exercise through a guided review of the PP manual, and (c) assignment of the next week's PP exercise. During the calls, the interventionist and participant will also review the next section of the treatment manual and prepare for the upcoming week's exercise.

**Positive Psychology Exercises.** The PP exercises used in this study were selected based on the qualitative study results from the first phase of this study (IRB: 17-154), their superior performance in our pre-pilot research and others' work with medical populations. They will be grouped into three modules focusing on a different psychological state:

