**22.0 Recruitment Methods**

Hospital (BWH) and Dana Farber Cancer Institute (DFCI) HSCT Program in Brookline, MA as was approved for protocol 17-154. Eligible study participants will be identified during the aforementioned weekly HSCT program meeting of HSCT attendings, which reviews all the upcoming scheduled admissions and discharges. Patients will be approached when they are medically stable after HSCT in their private hospital rooms at BWH for eligibility determination and to obtain consent. Upon agreement to participate in the study, contact will be maintained with patients from discharge date to day 90-120 of HSCT via three monthly phone calls to check in and to remind them study initiation. At the routine 100-day oncology visit at the DFCI Yawkey Building in Brookline, MA, self-assessment questionnaires will be obtained. Patients will also be given the option to complete self-assessment questionnaires via phone or mail.

DFCI HSCT program will be the source of the subjects for this study.

Eligible study participants will be identified during the weekly HSCT program meeting, which reviews all the upcoming scheduled admissions and discharges.

Patients will be approached based on approval by the HSCT oncologists at the transplant team meeting. Hence there aren't specific materials or advertisements to recruit patients.

Patients will not receive payments for participating in the study.

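### By default the outcome scales move from clinic completion before the intervention to phone or mail afterwards, so any mode effect is mixed into the average before-after change

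*Combined protocol and SAP*

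**What the plan says.** **Before the intervention.** Section 9.1 places the assessment at the routine visit around day 100, where the interventionist "will meet briefly with the patients in clinic to complete self-assessment questionnaires". Section 9.2 (Pre-intervention visit) puts it in a private clinic room, and Section 20.0 repeats that setting.

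Remote completion is allowed at this point, but on differing terms:
- Section 9.1 allows phone or mail as an exception: "For the rare situations when participants cannot complete these self-assessment questionnaires in person".
- Section 9.2 allows phone only, for scheduling reasons: "Patients will also be given the option to complete this visit over phone if in person visit cannot be coordinated".
- Section 22.0 attaches no condition: "Patients will also be given the option to complete self-assessment questionnaires via phone or mail".
- Section 7.1 does not say which assessment it means: "Patients will also be given the option to complete self-reported measures via mail vs. phone".

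**After the intervention.** Section 9.2 (Follow-up session) says "This will be done either via phone or mail depending on patient preference". The fuller Follow-Up Session text makes the phone the default: "a member of the study staff will call participants to repeat the self-report questionnaires that were administered at baseline". A paper packet is sent to those who would rather write. No in-person option is given.

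**Analysis.** Section 2.3 describes a non-randomized trial of 25 patients. Section 11.1 plans descriptive statistics and, for Aim 3, paired t tests, with non-parametric tests or effect sizes as possible alternatives. No section asks for mode to be recorded, held constant within a patient or allowed for in the analysis.

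**The concern.** A before-after comparison assumes that the instrument is applied in the same way both times. Here the usual participant fills in the scales at a clinic visit and later answers them to a caller, or on paper at home. If people answer mood, fatigue or quality-of-life items differently in those conditions, the difference appears as change over time. A control arm assessed in the same way would cancel it, and this trial has none.

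Hypotheses 2 and 3 both claim improvement at completion relative to baseline, and all six scales follow the same schedule. Mode at follow-up is the patient's choice, so the effect may also differ between participants. At stake is the interpretation of any mean change or effect size reported from these scales. The primary aim, feasibility and acceptability, is not affected.

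**Working it through.** The plan gives no figure to reproduce: it states no effect size, SD or mode effect. The main check is to follow one participant through the two assessments.

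**Possible paths**

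| Before | After | What changes |
|---|---|---|
| Clinic (default) | Staff phone call (default) | Setting, and probably format: own completion to spoken answers |
| Clinic | Mailed packet | Setting and staff presence; format perhaps not |
| Phone (exception) | Phone | Nothing in mode |
| Mail (exception) | Mailed packet | Nothing in mode |
| Phone or mail (exception) | The other remote mode | Format |

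Nobody assessed in clinic can have the same setting twice. Only participants who take a remote option beforehand can keep one mode. Section 9.1 expects few of these, while Section 22.0 sets no limit, so the share who switch cannot be derived from the documents. Nor do they say whether the clinic scales are on paper.

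**Illustration of size**

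Assumptions, none of them from the documents:
- mode shift d of 0.1 to 0.3, in SDs of the change score;
- share of participants affected, s, of 0.5 to 1;
- true change of zero, with the SD of the change score unaffected by the mix of modes.

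Inputs from the plan:
- two-sided tests at 0.05 (Section 11.1);
- 10 completers (Sections 11.2 and 23.0);
- alternatively 20, which is the 80% follow-up target of Section 1.3 applied to 25 (0.80 × 25 = 20).

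Formulas:
- Spurious mean change = d × s.
- Rejection probability = 1 − F(c) + F(−c), where F is the noncentral t distribution with n − 1 degrees of freedom and noncentrality d × s × √n, and c is the 97.5% point of the central t.

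| d | s | d × s | n = 10 | n = 20 |
|---|---|---|---|---|
| 0 | any | 0 | 5.0% | 5.0% |
| 0.1 | 0.5 | 0.05 | 5.2% | 5.5% |
| 0.1 | 1 | 0.10 | 5.9% | 7.1% |
| 0.2 | 0.5 | 0.10 | 5.9% | 7.1% |
| 0.2 | 1 | 0.20 | 8.8% | 13.6% |
| 0.3 | 0.5 | 0.15 | 7.1% | 9.8% |
| 0.3 | 1 | 0.30 | 13.6% | 24.7% |

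For scale, the 95% half-width for a mean change with 10 completers is about 2.26/√10, or 0.72 SD of the change score. The assumed bias lies well inside that. It differs from sampling error in that it does not shrink as more patients complete, which is why the n = 20 column is worse.

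The rejection rates apply where a paired t test is used, and Section 11.1 names that test for Aim 3 only. The shift in the mean applies to all six scales, whatever the test.

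**The case against.** **Impact is limited.** The primary aim is feasibility, the before-after comparisons are expressly unpowered, and with 10 completers sampling error exceeds any plausible mode effect. This stands and keeps the point modest. Low power does not, however, remove bias from a reported mean change.

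**Not everyone switches.** A reader might infer that every participant's change is contaminated. Sections 9.1, 9.2 and 22.0 all allow remote completion beforehand, and a move from clinic to mailed paper is smaller than one from clinic to phone. The statement holds for the average change on each scale, not for each patient.

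**Direction is unknown.** A reader might infer that phone answers would favour the intervention, the more so because Section 20.0 names the principal investigator, who is also the interventionist, as the only current staff member and so possibly the caller. The documents do not support a direction. The same person is present in clinic, after three rapport-building calls, and could colour the earlier answers. For those who choose mailed paper, staff contact falls at follow-up.

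**Other evidence exists.** The paired change is not the sole evidence for Hypothesis 2. Section 9.2 also collects happiness and optimism ratings around every weekly phone session. These do not replace the validated scales and do not serve Hypothesis 3.

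**No stated use for planning.** A reader might infer that a biased effect size will determine the size of the next study. The plan says only that this trial precedes a larger pilot and helps refine the intervention.

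**The remedy has a price.** Mailed packets could threaten the 80% follow-up target, and a phone fallback links mode to late response. Both are fair, and they are why the phone is kept as a fallback and mode is recorded.

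**Conclusion.** The point holds as a risk of bias of unknown size and direction. By default, mode or setting changes at the same time as the intervention is given, no control arm cancels the effect, and the plan neither records nor matches mode.

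Under the assumed shifts of 0.1 to 0.3 SD of the change score in half to all participants, the spurious mean change is 0.05 to 0.30 SD. The nominal 5% error becomes 5.2% to 13.6% with 10 completers and 5.5% to 24.7% with 20. If mode has no effect, or is the same both times, the bias is zero. These figures show scale only and are not estimates for this trial.

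Because the comparisons are exploratory, this is an inexpensive improvement and no ground for doubting the primary aim.

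**What to change.** 1. Make the written, self-completed form the default at both assessments, and say so for the clinic visit. Give participants the follow-up packet, already part of the plan, with the treatment manual, or mail it in the last session week.
2. Complete the scales by phone in two cases: when the packet is not back within a stated window, which protects the 80% target, and when the pre-intervention scales were done by phone, so that mode matches. Keep the staff call for the questions about experience in the study.
3. Record mode at each assessment in REDCap. Describe the paired change for same-mode and switched-mode participants separately. With about 10 completers this is descriptive only, so matching mode in advance matters more than the split.
4. Reconcile Sections 9.1, 9.2 and 22.0 on when remote completion is allowed before the intervention, and state which assessment Section 7.1 means.

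The cost is protocol wording, postage and one data field per assessment. The downside is slower returns and some phone fallback, so a few participants will still switch mode. A form completed at home also still differs in setting from one completed in clinic, so the change reduces the problem without removing it.
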